Table 4. Summary of study visits and procedures

	Screening	Baseline	Wk 1	Wk 2	Wk 3	Wk 4
Baseline Questionnaire (comorbidities, sociodemographics, tobacco and alcohol use, use of dietary supplements and urine output)		X				
Medical Chart Review (cause of CKD, comorbidities, urine albumin concentration)		X				
Medical Chart Review (medications)		X		X		X
Dietary Assessment (3-day food record)			X			
Anthropometrics (height)	X					
Anthropometrics (weight)	X			X		X
Fasting Blood Test (potassium)	X		X	X	X	X
Fasting Blood Test (phosphorus, calcium, magnesium, albumin, glucose, insulin, cholesterol, LDL-cholesterol, HDL-cholesterol, triglycerides, urea nitrogen, bicarbonate and C-reactive protein)		X		X		X
Blood Pressure (systolic and diastolic blood pressure)		X		X		X
Gastrointestinal Symptoms Questionnaire (frequency and severity of abdominal cramping, abdominal discomfort, indigestion, infrequent or difficult to pass bowel movements, flatulence, loose or watery stools in previous week)		X	X	X		X

10) Data and Specimen Banking

No samples will be stored for future analyses in this study.

11) Data Management

Information to be obtained from participants includes height and weight, blood pressure, medical history, blood tests, and self-administered questionnaires (sociodemographics, clinical and comorbid conditions/ management, cigarette and alcohol use and gastrointestinal symptoms). None of the data to be collected is considered sensitive in nature. Some of the participant data such as laboratory results will be linked to the participant's name. Other data (e.g., height, weight, blood pressure, medical history, and surveys) will be linked to the participant through a subject ID number. As a further measure to protect participants' privacy, different subject ID numbers will be used for study measurements and for coordinating the feeding component of the study. We will maintain separate files for identified and de-identified data in locked file cabinets in a locked office. Access to these data will be restricted to the PI ([name]), and study staff responsible for gathering data and maintaining research files. Data will be entered into a centralized database maintained on a secure server. Data

in these files will be linked to participants only through their ID number – this file will be maintained in a locked filing cabinet at [name]. All data collected will be used expressly for the purpose of the proposed study.

a. Overview.

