A descriptive analysis of all data collected will be performed using appropriate graphical and numerical exploratory data techniques. The information obtained from this preliminary investigation of the data will be used to: (1) assess data quality and completeness, (2) describe univariate distributions at baseline and follow up, and (3) create summary statistical data for outcome variables at each time point, including the proportion of participants with hyperkalemia. We will identify features of the data that may necessitate special analytic methods (e.g., excess zeros, missing data, departures from distributional assumptions, outliers).

For analytic analyses, we will examine: (1) changes in outcome variables (blood pressure, gastrointestinal symptoms, and fasting concentrations of potassium, phosphorus, calcium, magnesium, albumin, glucose, insulin, cholesterol, LDL-cholesterol, HDL-cholesterol, triglycerides, urea nitrogen, bicarbonate and C-reactive protein), and covariates (weight, medications, dose of Patiromer) between baseline and the end of each diet phase, and (2) relationships between the changes in outcome variables and covariates. Changes in study outcomes will be graphically depicted using means \pm SD or median (IQR) as measures of central tendency and variance. Changes in study outcomes will be analyzed using repeated-measures analysis of variance with post-hoc Tukey HSD test. Because of the small sample size, covariates will be reported instead of being included in a multivariable model. Depending on the types of covariate and outcome of interest, subgroup analyses may be performed with these participants removed from the dataset. For example, if a participant's dose of phosphorus binder medications changed during the study, the analysis of phosphorus concentrations would be conducted with/without this participant. Given the short duration of this study (4 weeks) in relation to typical monitoring of patients with stage 3B-4 CKD, we expect that that few, if any, subgroup analyses will be required.

12) Provisions to Monitor the Data to Ensure the Safety of Subjects

Protection against Risk.

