Prior to the intervention, participants will receive education on the signs and symptoms of hyperkalemia; muscle weakness, abnormally slow or rapid heart rate, and heart palpitations (from Patient education: Hyperkalemia (the basics); UpToDate.com)⁶. Participants will be directed to monitor themselves for these conditions, and to go to the emergency room if they start experiencing them, making sure to notify the emergency department staff about their participation in the study. Standard treatment for acute episodes of hyperkalemia includes intravenous infusions of calcium gluconate and glucose/insulin, often followed by polystyrene sulfonate or emergent dialysis to remove excess potassium. The emergent treatment of adverse events will be at the discretion of the attending physician. In the event of any admission to the emergency room (even if determined to be unrelated to hyperkalemia), participants will be asked to alert the study PIs as soon as possible.

The intervention contains several features to lower the risk of hyperkalemia. For one, the research diets will be prepared for participants to provide control over the dietary potassium exposure. We will use the feeding study approach that gradually increases dietary potassium in a step-wise manner in order to prevent large shifts in dietary potassium intake. During phase I, participants will be stabilized on a plant-rich diet that restricts dairy products and excludes fruits and vegetables that are high in potassium. This closely approximates the current dietary recommendations for CKD patients with hyperkalemia, but does include plant-based foods from the Protein Foods Group (legumes, nuts, seeds), which are high in potassium (>200 mg/serving). However, compared to the typical Western diet, plant-rich diets are more alkaline, and are higher in fiber, factors that are thought to help control serum potassium concentrations⁴. After a week of consuming this diet, high-potassium fruits and vegetables will be introduced, and make up half of the fruit and vegetable servings. We will closely monitor participants’ adherence to the research diets through daily food records to ascertain their adherence with the study diets – participants that are determined to be non-adherent with the research diets at the end of phase I (defined in section 14) will be withdrawn from the study.

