Lastly, participants in the study are at risk of breaches of confidentiality. A variety of measures will be used to prevent breaches of confidentiality. First, all study staff will be trained in the NYULMC Practice Fundamentals, which include training in issues of confidentiality. Additionally, all study staff will be required to sign a confidentiality agreement. Although study staff may have access to sensitive information about the participant as recorded in their medical record, only that information pertinent to the study outcomes will be abstracted from the medical record. Data will be maintained as described above (see section 12). We will take steps to avoid participants' perceptions of coercion in the recruitment process.

13) Withdrawal of subjects

As mentioned previously, participants may be withdrawn from the study without their consent in the event that they become pregnant, or they are non-adherent with the research diets. Non-adherence to the research diets will be defined as consumption of >25% of energy from non-research diet foods, which will be assessed at the end of phase I of the study. In the event that involuntary withdrawal is required, participants will be referred back to their treating physician of record for evaluation and management. Data collection will cease at the time of withdrawal.

14) Risks to subjects

Most of the risks associated with this study are outlined in section 13 along with corresponding measures to protect against these risks (include hyperkalemia, patiromer side effects and interactions with medications, and breach of confidentiality). Blood tests will be drawn for this study, which are sometimes accompanied by bruising, bleeding, and minor tenderness at the puncture site. Participants will be made aware of all of these risks prior to enrolling in this study.

15) Potential Benefits of the Proposed Research to the Subjects and Others

Participants may experience some temporary improvement in cardiometabolic risk factors and serum potassium concentrations related to intervention; however, this is not guaranteed. Moreover, any temporary improvements in these conditions are unlikely to have any lasting benefits to participants.

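### Does Section 11 leave unreported whether participants ate the high-potassium produce before the week 4 potassium was measured?

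*Combined protocol and SAP*

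**What the plan says.** Section 9 (Design) puts the high-potassium fruits and vegetables in phase II only, weeks 3 and 4. Section 12 describes the same step: "After a week of consuming this diet, high-potassium fruits and vegetables will be introduced, and make up half of the fruit and vegetable servings".

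Diet data are gathered during feeding. Section 9 (Research Diets) tells participants to eat what is supplied and to write down departures from it. Section 12 says the study will monitor "adherence to the research diets through daily food records to ascertain their adherence with the study diets". Section 13 gives the only numerical definition of non-adherence, "defined as consumption of >25% of energy from non-research diet foods, which will be assessed at the end of phase I of the study", and uses it as a ground for withdrawal.

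Section 11 says of the data to be gathered: "Information to be obtained from participants includes height and weight, blood pressure, medical history, blood tests, and self-administered questionnaires". Its Overview opens with a general promise: "A descriptive analysis of all data collected will be performed using appropriate graphical and numerical exploratory data techniques". That description has three uses: checking quality and completeness, describing univariate distributions at baseline and follow-up, and a third, to "create summary statistical data for outcome variables at each time point, including the proportion of participants with hyperkalemia". The Overview then turns to changes in the outcomes and in "covariates (weight, medications, dose of Patiromer) between baseline and the end of each diet phase", and to how the two are related. It adds: "Because of the small sample size, covariates will be reported instead of being included in a multivariable model".

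**The concern.** The hypothesis in Section 2 concerns patients who actually consume the diet, and Section 15 hopes the results will bear on whether high-potassium plant foods need to be restricted. A normal week 4 potassium supports that only if the produce was eaten. Meals are eaten away from the clinic, and substitutions from an approved list are allowed.

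The parts of Section 11 that name variables leave diet out: it is neither an outcome nor one of the three covariates. The list of information to be obtained does not mention food records, and the summary statistics in the third use are for outcomes. The only adherence threshold is applied before the produce arrives. It also counts energy from outside foods, so a participant who left the supplied produce on the plate and replaced it with nothing would not breach it. On these passages alone, a participant who ate the produce and one who did not could look the same in the report, although records exist that could tell them apart.

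**Working it through.** The plan gives no figure to reproduce: it states a sample size of 10 with no power, effect size or standard deviation. The check compares what is collected with what Section 11 promises to describe.

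**1. Timing of the threshold.** Inputs are from Section 9 (Design): phase I is week 2 and phase II is weeks 3 and 4.
- Feeding days: 7 + 14 = 21.
- Days elapsed when the threshold is applied: 7 of 21 (33%), and 0 of the 14 phase II days.

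This counts days covered by a withdrawal rule. It does not count days on which diet is recorded. The monitoring sentence in Section 12 refers to the research diets in the plural, and Table 3 defines two, one for each phase.

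**2. Does the general promise reach the food records?** Section 11 says a description of all collected data will be carried out, which is a commitment. Food records and noted deviations are collected data. Only the third of the three uses is confined to outcomes. The second, distributions at baseline and follow-up, is not, and the first, quality and completeness, also applies to the records.

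**3. Does the list of information rule them out?** The list is introduced as what the information includes, so it is not exhaustive, and it opens a paragraph mainly about privacy and record linkage. It also omits patiromer dose, which the Overview names as a covariate. Absence from the list therefore does not show that an item will go unreported.

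**4. Would uneaten food be recorded?** Participants are told to eat what is provided and to record any deviation. Leaving supplied food is most naturally a deviation under that instruction, although the plan does not say so in terms.

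**5. What would differ in the results?** The planned test is repeated-measures analysis of variance on potassium with Tukey comparisons. Covariates are reported and not modelled. Naming an intake variable would add a descriptive column and leave the test, its inputs and the withdrawal rule as they are.

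**6. Can a size be given?** Suppose no participant were hyperkalemic at week 4. The exact two-sided 95% upper limit for 0 of n is 1 − 0.025^(1/n):
- n = 10: 30.8%
- n = 8: 36.9%
- n = 7: 41.0%
- n = 5: 52.2%

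The smaller values of n assume that 2, 3 or 5 of the 10 left the produce uneaten. The documents support none of these counts. The calculation also assumes zero events and selects on behaviour after baseline. It shows that fewer informative participants give a wider limit, which holds in any study. It does not measure a defect in this plan.

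**The case for a change.** The best case for a change is that a general promise is weaker than a named variable. The Overview calls the descriptive step preliminary and defines no intake measure. A univariate distribution of intake would not show whether the particular participant with a normal week 4 potassium was one who ate the produce. Table 4 marks a dietary assessment at week 1 only. Table 3 sets the diets as fractions of food groups with no amount of potassium, so even with full adherence the step from phase I to phase II is not quantified. The remedy would also be cheap: a short per-participant listing from records already kept.

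Part of this stands. Section 11 names no intake or adherence variable and does not require phase II consumption to be set beside the week 4 potassium. The 25% rule would miss produce left uneaten at any time.

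It does not carry the conclusion. The week 1 row in Table 4 is the three-day record of usual diet, whereas the daily records in Section 12 are a separate activity on the research diets. With at most ten participants, showing adherence next to potassium is an obvious step for anyone writing up a controlled feeding study, and nothing in the plan prevents it. Such a table would still rest on self-report and would not isolate the effect of patiromer, since the design has no comparison group.

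**Conclusion.** No change to the plan is needed. The gap is one of specificity: intake in weeks 3 and 4 is recorded and falls under a general commitment to describe all data, but it is not named or explicitly paired with the week 4 potassium. No rule in the plan gives a wrong answer because of this, and the potassium analysis would be identical with or without a named intake variable. The documented facts amount to none of three named covariates being dietary and a withdrawal threshold that precedes all 14 phase II days. The effect on the conclusions cannot be sized, because the number of participants who would not eat the produce is unknown.

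This rests on two readings: that the daily food records continue through both research diets, as the plural in Section 12 indicates, and that the investigators summarise them as Section 11's opening sentence says. Analysts can choose sensible descriptive measures, such as servings of the produce eaten and share of energy from outside foods, when they prepare the report.

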Principal Investigator: [name]

Study Number: 17-00051

NCT Number: NCT03183778

1) **Protocol Title**

Use of patiomer to transition chronic kidney disease patients with hyperkalemia to a plant-rich diet

2) **Objectives**

The purpose of this proof-of-concept controlled-feeding study is to determine whether patiomer (Veltassa®, Relypsa, Inc., Redwood City, CA) can be used to maintain normal serum potassium concentrations in chronic kidney disease (CKD) patients who are transitioned to a plant-rich diet. We hypothesize that patiomer can be titrated to maintain serum potassium concentrations in the normal range, allowing CKD patients to consume a plant-rich diet without developing hyperkalemia. If successful, we plan to conduct a randomized clinical trial to determine the quality of life and health outcomes of CKD patients with hyperkalemia undergoing an intensive behavioral intervention to promote a low-potassium diet, or a plant-rich diet plus patiomer.

3) **Background**

An estimated 22.5% of adults 60 years and older in the U.S. have stages 3-5 CKD¹. Individuals with stages 3-5 CKD are at increased risk of high blood potassium concentrations (hyperkalemia), which in severe cases can disrupt the normal contractility of the heart². Several factors are thought to contribute to hyperkalemia in CKD patients, in particular diabetes, dietary potassium intake, and medications that inhibit the renin-angiotensin-aldosterone system (RAAS inhibitors, which include angiotensin converting enzyme inhibitors and angiotensin 2 receptor blockers; ACEi and ARBs)^{3,4}. Given the potential health consequences of hyperkalemia, stages 3-5 CKD patients, even those without hyperkalemia, are often directed to follow a low-potassium diet⁴.

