Unfortunately, following a low-potassium diet involves limiting or avoiding many plant-based sources of potassium, including nuts, seeds, legumes, and high-potassium fruits and vegetables. With accompanying dietary restriction requirements for sodium, phosphate and protein, the diet can be burdensome and unpalatable for the patients, and can make it difficult to obtain essential nutrients⁴. In addition to providing potassium, high-potassium plant foods are important sources of dietary fiber, organic anions (potential base), antioxidants and other phytochemicals (e.g., phytosterols), and therefore, a low-potassium diet may contribute to hypertension (low potassium), constipation and diarrhea (low fiber), dysglycemia and dyslipidemia (low fiber and other phytochemicals), metabolic acidosis (low organic anions), oxidative stress and inflammation (low antioxidants and other phytochemicals)⁴.

Patiomer is approved by the U.S. Food and Drug Administration (FDA) for the treatment of hyperkalemia, and has been demonstrated to be effective in treating hyperkalemia in CKD patients⁵. However, the potential of this new therapy for allowing CKD patients to liberalize their diets, and the potential health benefits of following a plant-rich diet in advanced CKD are yet unexplored.

4) **Inclusion and Exclusion Criteria**

The focus of the study is to: a) evaluate the efficacy of patiomer for managing serum potassium concentrations in CKD patients as they are transitioned to a plant-rich diet that includes high-potassium fruits and vegetables, and b) evaluate the impact of a plant-rich diet on health outcomes in CKD patients. We will recruit 10 CKD patients with persistently elevated serum potassium concentrations in New York City.

i. Inclusion criteria. In order to be eligible for the study, the individual must meet the following criteria:

a) 19-80 years of age

b) Stages 3-4 CKD (estimated glomerular filtration rate (eGFR) of 15-59 mL/min/1.73m², not

treated with dialysis)

c) No prior treatment with patiromer

d) Mild hyperkalemia (potassium 5.1 to <6.5 mEq/L) on one of the last two blood tests

e) No prior episodes of moderate-severe hyperkalemia (potassium \geq 6.5 mEq/L) in the past 6 months

f) Deemed appropriate for the intervention by the patient’s nephrologist, considering the patient’s prognosis, cognition and pending treatments (e.g., dialysis)

ii. Exclusion criteria. We will exclude from participation patients with the following characteristics:

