a) Change in medications that alter potassium homeostasis (e.g., RAAS inhibitors, diuretics, β -blockers) in the last month

b) Diagnosed with bowel diseases or syndromes (e.g., bowel obstruction, major GI surgery, short-bowel syndrome, irritable bowel syndrome, inflammatory bowel disease, chronic diarrhea)

c) Dietary restrictions (e.g., allergies) or otherwise unable/unwilling to adhere to study diets (excludes dietary restrictions on high-potassium foods)

d) Pregnant (females) or planning to become pregnant (males and females) during the study

If at any point during the study (including baseline) a participant has moderate-severe hyperkalemia (potassium \geq 6.5mEq/L), or if a participant becomes pregnant during the study, they will be withdrawn from the study.

Inclusion of women and minorities

Given the pilot nature of the intervention and small sample size (n=10), the study population will not be representative of the CKD population, and will have insufficient power to detect differences in intervention effects by sex and race/ethnicity. To our knowledge, plant-rich diets, such as those being investigated in this study, have similar health effects by sex and race/ethnicity. No individual will be excluded from the study on the basis of sex or race/ethnicity alone, and we will attempt to obtain a sample that reflects the demographics of our source population.

5) Study-Wide Number of Subjects

We will recruit a total of 10 individuals to the study. We have secured the support of the New York Harbor VA Healthcare System, which served approximately 250 non-dialysis CKD patients in the New York City area, as well as the Division of Nephrology at NYU Langone Health. It is estimated that approximately 10% of these patients have hyperkalemia. Thus, we have no concerns about our ability to access and recruit the required number of participants for this study. The estimate demographic breakdown of patients at the renal clinic are 95% male with 40% white, 25% black, 20% Hispanic, 10% Asian, and 5% other racial/ethnic background. The planned enrollment is outlined in Table 1.

Table 1. Planned enrollment report

Racial Categories	Ethnic Categories				Total
	Not Hispanic or Latino		Hispanic or Latino		
	Female	Male	Female	Male	
American Indian/ Alaskan Native	0	0	0	0	0
Asian	0	1	0	0	1
Native Hawaiian or Other Pacific Islander	0	0	0	0	0
Black or African American	0	2	0	1	3
White	1	3	0	1	5

More than 1 race	0	1	0	0	1
Total	1	7	0	2	10

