6) Study-Wide Recruitment Methods

Potential participants will be identified using two recruitment methods: 1. Referral by the patient's nephrologist, and 2. DataCore directed search of electronic medical records. Nephrologist referral patients will be obtained from the New York Harbor VA Healthcare System, NYU Langone Health, and Bellevue Hospital. The DataCore directed search of electronic medical records will be limited to patients of nephrologists in the Division of Nephrology who have an episode of mild hyperkalemia in the past 6-months. Once identified using the electronic medical record search, the patient's nephrologists will be notified about their potential eligibility. Per the study inclusion criteria, nephrologists will be asked to confirm that the patient is appropriate for the study.

- (a) [name] or [name] will review each section of the written consent form with the referred participant, ask the participant if they understand each section, and clarify any questions they may have. The participant and the person obtaining consent will sign and date the consent form. Copies of the consent, which includes the contact information of the PI ([name]), will be provided to the participant and sent to the patient's nephrologist. Informed consent will be considered an ongoing process throughout the study, and participants' questions regarding their rights and responsibilities will be addressed whenever they occur.
- (b) Once enrolled, [name] and [name] will meet to verify that the participant meets the inclusion/exclusion criteria. This information will be obtained from the patient's electronic medical record.
- (c) Study staff will contact eligible patients, and schedule a fasting screening appointment (at least 8 hours of fasting).

A fasting blood sample will be obtained at the screening visit, and analyzed for potassium. If this test is in the range of mild hyperkalemia (potassium 5.1 to <6.5 mEq/L), the participant will be deemed to have persistent hyperkalemia, and be accrued. Otherwise they will be deemed ineligible, and excluded from the study. Regardless of enrollment status, all eligible patients who are invited to participate in the study will be reimbursed \$25.00 for time and travel expenses incurred by attending the screening visit.

7) Study Timelines

We will recruit 10 participants. Given the intensiveness of the intervention, no more than two participants will be enrolled in the intervention at a time.

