8) Study endpoints

Among 10 stages 3-4 CKD patients with persistent, mild hyperkalemia, we will evaluate, in a quasi-experimental, controlled feeding study, the efficacy of patiomer for maintaining normal serum potassium concentrations when following a plant-rich diet that includes high-potassium fruits and vegetables, as well as the effects of this diet on health outcomes. The participants will be transitioned gradually to a plant-rich diet, as outlined further below.

The interventions will be evaluated primarily in terms of serum potassium concentrations, but health outcomes will also be assessed, including blood pressure, gastrointestinal symptoms, and fasting concentrations of phosphorus, calcium, magnesium, albumin, glucose, insulin, cholesterol, LDL-cholesterol, HDL-cholesterol, triglycerides, urea nitrogen, bicarbonate and C-reactive protein. For all parameters, baseline values will be compared to values at the end of each diet phase (weeks 2 and 4).

9) **Procedures involved**

a. Design.

We will conduct an unblinded, quasi-experimental, controlled feeding study, which will be coordinated through the New York University – Health and Hospitals Corporation Clinical and Translational Science Institute (CTSI). Throughout the study, participants will be prescribed patiromer by the study nephrologist ([name]), which will be administered through the CTSI pharmacy. After a 1-week stabilization period, in which participants are prescribed Patiromer while following their usual diets, the feeding component of the study will occur in two phases. During the first phase (week 2), participants will be transitioned to a plant-rich renal diet, which contains moderate protein (10-15% of kcal), restricts dairy products (≤ 1 serving/day), and eliminates high-potassium fruits and vegetables. During the second phase (weeks 3 and 4), the diet will be altered to provide at-least half of fruits and vegetables from high-potassium sources. To reduce participant burden, meals will be delivered to participants by Portable Chef (New York, NY) three times per week.

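### The hypothesis is about potassium staying in the normal range, but the only named test compares means, mainly against a screening value that must be high for entry; the in-range proportion should lead, with an exact interval

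*Combined protocol and SAP*

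**What the plan says.** Section 2 (Objectives) states the aim in terms of range: "We hypothesize that patiomer can be titrated to maintain serum potassium concentrations in the normal range". Section 8 (Study endpoints) repeats it as "the efficacy of patiomer for maintaining normal serum potassium concentrations when following a plant-rich diet". Section 2 also names the next step: "If successful, we plan to conduct a randomized clinical trial".

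Section 11, a. Overview, names one inferential method for every outcome, including potassium: "Changes in study outcomes will be analyzed using repeated-measures analysis of variance with post-hoc Tukey HSD test". Section 8 sets the comparison: "For all parameters, baseline values will be compared to values at the end of each diet phase (weeks 2 and 4"). Section 9.b.iii gives the same comparison for potassium, with screening as the starting point. Table 4 marks no potassium test at the baseline visit, so the screening test is the only pre-treatment study value.

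That value is an entry condition. Section 6 accrues a participant on it: "If this test is in the range of mild hyperkalemia (potassium 5.1 to <6.5 mEq/L"). Section 4 also asks for an earlier raised value: "Mild hyperkalemia (potassium 5.1 to <6.5 mEq/L) on one of the last two blood tests".

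Section 11 lists the proportion of participants with hyperkalemia at each time point among the descriptive summaries. It gives no interval and no lower limit for a normal value. The 3.8–5.0 band in Table 2 (section 9.a.i) drives dosing actions and is not linked to the endpoint.

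Withdrawal criteria exist. Section 4 covers high potassium ("If at any point during the study (including baseline) a participant has moderate-severe hyperkalemia", defined there as ≥6.5 mEq/L) and pregnancy. Sections 12 and 13 cover diet non-adherence, judged at the end of phase I. Data collection stops at withdrawal, and nothing says how these participants count in the analysis.

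**The concern.** The question is how many participants are in range while eating the diet. The named test asks whether mean potassium has moved from a value selected to be above range. The two can disagree in three ways.

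- Mean potassium can fall significantly while many participants are still at or above 5.1.
- Because entry depends on the screening value itself, later values tend to be lower even if nothing works (regression to the mean). Change from screening therefore overstates the treatment effect.
- The contrast that isolates the step to high-potassium produce, week 2 versus week 4, is covered by Tukey. With 10 participants, however, failing to reject says little about whether control was maintained.

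A randomized trial is to follow if this study succeeds. The figure that bears most directly on that decision is planned without any statement of its uncertainty, and its denominator is undefined if anyone is withdrawn.

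**Working it through.** The plan gives no power or precision calculation, so there is no figure of its own to reproduce.

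**Inputs from the documents.** n=10 (sections 4 and 5); screening 5.1 to <6.5 (section 6); one of the last two tests in the same band (section 4); potassium at screening and weeks 1–4 (Table 4). The cut of 5.1 for hyperkalemia is inferred from the entry band.

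**Assumptions.** The documents give no SD, effect size, alpha or dose response. The base case takes within-person SD 0.3, between-person SD 0.35, mean 5.0 before selection, two-sided 0.05, values rounded to 0.1, and screening, week 2 and week 4 in the ANOVA. Ranges below cover two selection rules: screening alone, and screening plus one of two prior tests. Titration, where included, is modelled as an extra 0.3 fall for those ≥5.1 at week 2.

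**Tukey threshold.** HSD = q(3,18) × √(MSE/n) = 3.61 × √(0.3²/10) = 0.34 mEq/L.

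**Selection alone.** With zero treatment effect, mean potassium falls by 0.14–0.17 from screening to week 4. That contrast is significant in about 9–13% of trials, although Tukey is meant to hold the error over all three contrasts to 5%.

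**Significant fall versus in-range control.** A true fall of 0.3 becomes an expected observed fall of 0.3 + 0.14 to 0.3 + 0.17, that is 0.44–0.47, which exceeds 0.34. Simulation gives:

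| True fall | Titration | Screening vs week 4 significant | Participants ≥5.1 at week 4 |
|---|---|---|---|
| 0.3 | none | 81–86% | 38–43% |
| 0.3 | extra 0.3 | 95–96% | 27–30% |
| 0.6 | none | >99% | 15–18% |
| 0.6 | extra 0.3 | >99% | 11–13% |
| 0.9 | none | >99% | 4–5% |

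Varying the mean over 4.8–5.2, the within-person SD over 0.2–0.4 and the between-person SD over 0.25–0.45 gives these shares still ≥5.1:

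- Fall 0.3: 14–61% without titration, 10–42% with it.
- Fall 0.6: 2–33% without titration, 1–25% with it.

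**Maintenance.** Suppose potassium falls 0.6 by week 2 and then rises 0.3 by week 4. The share ≥5.1 goes from 15–18% to 38–43%. The rise of 0.3 is below the threshold of 0.34, and the contrast detects it in about 44% of trials. With titration, the share reaches 33–38% and detection is 30–32%. The paired 95% CI half-width is t(9) × SD × √2/√n = 2.262 × 0.3 × √2/√10 = 0.30, so an observed difference of zero would still be compatible with a rise of about 0.3.

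**Exact intervals (no SD assumed).** Clopper-Pearson limits are the 2.5% point of Beta(x, n−x+1) and the 97.5% point of Beta(x+1, n−x). For 10/10 the lower limit is 0.025^(1/10) = 0.69.

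- 10/10: 69–100%
- 8/10: 44–97%

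**Denominator.** If 2 of 10 leave and 7 of the other 8 are in range, the result is 7/8 = 88% (47–100%) among those measured, or 7/10 = 70% (35–93%) with withdrawals counted as not in range.

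**The case against.** The strongest reply is that the key output is already planned. Section 11 commits to the proportion with hyperkalemia at each time point, so a report showing a significant fall would also show the share still high. Any reader can compute an exact interval from a count out of 10. Descriptive reporting is ordinary for a proof-of-concept study of this size, and the interval is too wide to settle the matter. This largely stands: the gap is in emphasis, definition and stated uncertainty, and the analysis is not absent.

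Two stronger readings are tempting, and the documents support neither. A reader might infer that the sponsor will declare success on a significant ANOVA, or maintenance on a non-significant contrast. No section ties success to a p-value or says a null contrast will be read that way. A reader might also infer that withdrawal is unregulated. Sections 4, 12 and 13 set criteria; what is missing is only how withdrawn participants are counted. That gap concerns mainly diet non-adherence. Under the base assumptions about 0.05% of participants would reach ≥6.5 at a fall of 0.3 (at most about 2% over the range tried), and section 12 has such episodes reviewed.

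The lower limit is also a small matter numerically: at a fall of 0.6, about 0.7–1.4% of week-4 values would be below 3.8. It still belongs in the definition, because a summary of hyperkalemia alone counts a low value as a success.

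**Conclusion.** The concern holds in limited form. The mismatch between a hypothesis about range and a test of means against a selected-high starting value is documented and does not depend on any assumed number. Its size does. It is material for small falls (0.3: 27–43% still ≥5.1 while 81–96% of trials are significant) and modest for large ones (0.6: 11–18%; 0.9 without titration: 4–5%). These figures rest wholly on assumed SDs, means, effects and titration response, and the ranges over other plausible inputs are wide. The exact intervals rest on none of these.

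It would go too far to conclude that the planned ANOVA is invalid or that the study cannot inform its question: the data needed are collected and a one-sided version of the right summary is planned. This is a worthwhile, inexpensive correction to make before the data are analyzed.

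**What to change.** In sections 8 and 11:

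- Make the lead estimate the number and proportion of participants whose week-4 fasting potassium lies in a range with both limits stated, declared by the sponsor for analysis only, with an exact (Clopper-Pearson) 95% CI. Report the same at week 2.
- Use one denominator: everyone who starts patiromer. Count anyone without a week-4 value as not in range and list them by reason. Add one sensitivity analysis in participants with a week-4 value.
- Keep mean change from screening and the paired week 2 to week 4 difference as secondary estimates with 95% CIs. State that change from screening includes regression to the mean, and that a non-significant contrast is not evidence of maintenance.
- Reconcile the phase-end weeks so that the analysis time point is unambiguous. The opening of section 9.b puts the ends of phases I and II at weeks 1 and 3; section 8 and the later parts of 9.b put them at weeks 2 and 4.

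The cost is a few sentences, with no new visits or samples. The downsides are a wide interval at n=10 and a lower headline figure when withdrawals count as not in range. That rule also mixes diet adherence with potassium control, which is why the sensitivity analysis and the list of reasons are needed.
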